7.2.2 Efficacy

To ensure a homogeneous radiological evaluation, all MRI images will be retrospectively centrally reviewed.

The following criteria will be used to determine the efficacy of study treatment.

Progression Free Survival (PFS): PFS is defined as the number of days from consent to the date of earliest disease progression based on Response Assessment in Neuro Oncology (RANO) criteria (as determined by the Investigator) or to the date of death, if disease progression does not occur. In group C, patients for whom neither death nor progression have been documented will be censored on the date of the last radiological assessment if they have no post anti-cancer therapy. If a patient has other post anti-cancer therapy prior to progression or death, the data will be censored at the date of last radiological assessment prior to or on the start date of post anti-cancer therapy. In group A and B, post anti-cancer therapy is not collected. The data will be censored at the date of the last radiological assessment. In all groups, if a patient with no post-baseline radiological assessment did not experience progression nor died, then the data will be censored at the date of enrollment.

PFS at 6 months (PFS-6) is the PFS rate at 6 months extracted from the PFS Kaplan Meier distribution based on RANO criteria (as determined by the Investigator)

Overall Survival (OS): OS is defined as the number of days from consent to the date of death due to any cause. If a patient has not died, the data will be censored at the last date documented to be alive.

OS at 9 months (OS-9) is the OS rate at 9 months extracted from the OS Kaplan Meier distribution.

Objective (ORR) and complete (CR) response rates are the proportions of patients with best overall response PR+CR or CR (see below) respectively.

Duration of objective (complete) response (DOR): DOR is determined as the number of days from the time point where the overall response PR or CR (CR) was first seen to the earliest date of detection of disease progression based on RANO criteria (as determined by the Investigator) or to the date of death, if disease progression does not occur. The same censoring rules defined above for PFS are applicable.

A success is defined as a patient achieving either confirmed CR or PR (> 4 week) or free of progression at 6 months.

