4. For patients receiving antiangiogenic therapy, significant increase in T2/FLAIR nonenhancing lesion may also be considered progressive disease. The increased T2/FLAIR must have occurred with the patient on stable or increasing doses of corticosteroids compared with baseline scan or best response after initiation of therapy and not be a result of comorbid events (e.g., effects of radiation therapy, demyelination, ischemic injury, infection, seizures, postoperative changes, or other treatment effects).

If the evidence of PD is equivocal (target or non-target lesions), treatment may continue until the next assessment, but if PD is confirmed at the next follow-up, the earlier date must be used as the date of progression.

In case non-measurable tumor is left after surgery i.e. tumor less than 10x10 mm, unequivocal progression of non-target lesion may be accepted as evidence of disease progression, where the overall tumor burden has increased sufficiently to merit discontinuation of treatment. Modest increase in the size of a non-target lesion is NOT considered unequivocal progression. If the evidence of PD is equivocal (target or non-target), treatment may continue until the next assessment, but if confirmed, the earlier date must be used as the date of progression. This implies that in case of gross total resection of the

enhancing lesion, if at follow up minimal enhancement of unclear significance arises, treatment may continue until further follow-up gives unequivocal evidence of tumor progression.

Stable Disease (SD):

This occurs if the patients did not qualify for complete response, partial response, or progression (see above) and requires: 1) No meaningful change in the appearance of the FLAIR/T2 images compared to baseline or to the nadir (point with the smallest FLAIR/T2 abnormalities) if a decrease occurred.

Evaluation of response, treatment decision and central review:

- For this trial, the primary measure of response and progression will be determined by the locally assessed response according to the RANO criteria. The time point of progression will be determined at the sites, although the centers in Zurich and Vienna (Reference Neuroradiology) will be happy to provide support.
- Study treatment is completed at the time of first progression. Follow-up until death or the end of data acquisition is required within this trial.

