These estimates will be presented both based on investigator and centrally reviewed progression data.

- Overall survival

In the efficacy population:

The OS rate at 9 months (OS-9), 1 year (OS-12) and the median will be extracted from the Kaplan-Meyer OS curve. For OS-9 and OS-12 95% two-sided confidence intervals will be computed based on Greenwood's formula. For the median the Reflected Method will provide 95% two-sided confidence intervals.

- Response and duration of response

In the efficacy population:

The best overall response will be presented in contingency table with numbers and percentages. The objective response (CR+PR) and complete response (CR) rates will be reported with exact (binomial) 95% two-sided confidence interval.

Duration of objective response and complete response will be estimated using Kaplan-Meier methodology. Median duration of objective and complete response with corresponding 95% two-sided confidence interval provided by the Reflected Method will be displayed.

These estimates will be presented both based on investigator and centrally reviewed response data.

- Success rate

In the efficacy population:

The success rate will be reported with exact (binomial) 95% two-sided confidence interval.

Success rate will be presented both based on investigator and centrally reviewed response data.

- Neurologic progression free survival

In the efficacy population:

The NPFS rate at 6 months (NPFS6) and the median NPFS will be extracted from the Kaplan-Meyer PFS curve. For NPFS6, 95% two-sided confidence intervals will be computed based on the Greenwood's formula. For the median the Reflected Method will provide 95% two-sided confidence intervals.

- Comparison of PFS by local investigator and by central review and comparison of NPFS and CDFS.

In the efficacy population:

The differences of times to event between these estimates will be tabulated.

- Safety and tolerability

In the safety population:

The safety and tolerability analyses will be presented at baseline and up to 30 days after the last administration of study drug. Baseline will include all information recorded up to the nearest date prior to or at randomization. Exceptionally in absence of this assessment, the first assessment performed after randomization but before start of protocol treatment can be considered as baseline.

Baseline laboratory and AE grades will not be accounted for in whole treatment safety analyses.

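### The Group C comparisons of local with central PFS, and of NPFS with CDFS, tabulate time differences without handling event status, so unconfirmed local progressions are not counted

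*Combined protocol and SAP*

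**What the plan says.** Section 8.2.2 (Group C, efficacy population) lists a "Comparison of PFS by local investigator and by central review and comparison of NPFS and CDFS". The whole method is: "The differences of times to event between these estimates will be tabulated". It does not state whether differences are per patient or between summary statistics, which patients enter, or what happens to censored times. No cross-table of event status and no agreement measure is planned.

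The same section covers PFS6 and median PFS from Kaplan-Meier: "These estimates will be presented both based on investigator and centrally reviewed progression data". Response, duration of response and success rate are also shown on both sources.

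Section 7.2.2 sets the PFS times. Group C patients without an event "will be censored on the date of the last radiological assessment if they have no post anti-cancer therapy". If new therapy comes first, "the data will be censored at the date of last radiological assessment prior to or on the start date of post anti-cancer therapy". PFS runs to progression "or to the date of death, if disease progression does not occur".

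On follow-up, section 7.2.5 says: "Study treatment is completed at the time of first progression". Section 6.3.3 continues three-monthly MRI only in patients who have not progressed. Section 6.3.1 requires one further brain MRI at the end-of-study visit, within 30 days (±5) of the last dose.

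**The concern.** A progression time and a censoring time are different kinds of number, and subtracting one from the other loses that difference. The local call largely decides when scanning stops, so a local progression that the central readers do not accept may leave them no later scan. Their time is then censored on the very date of the local event. In a table of differences, that patient cannot be told apart from one in whom both assessments called progression on that date.

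At stake is the basic result of a retrospective central read: how many local progressions were not confirmed, and how many central progressions were not called locally. Progression is the primary endpoint of this open-label, single-arm group and is assessed locally, so a reader will look for those counts.

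**Working it through.** **1. The plan's own figures.** This point rests on no stated figure. The only Group C design figures are in section 8.1.1: 45 evaluable patients, cut-off 13, P0 = 20%, P1 = 40%, α = 0.10, β = 0.05, total 50. Exact binomial: P(X ≥ 13 | 45, 0.20) = 0.0995 and P(X ≥ 13 | 45, 0.40) = 0.9554; 45/0.9 = 50. All reproduce, and nothing below changes them.

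**2. Worked patients.** Assumption: central PFS uses the section 7.2.2 Group C rules with the central progression date in place of the local one. Each patient has a local progression on day 56 that central review rejects. Later dates are illustrative. Difference = central time − local time.

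| What follows day 56 | Central time | Difference |
|---|---|---|
| No later scan, new therapy day 70 | 56, censored | 0 |
| No later scan, no new therapy, alive | 56, censored | 0 |
| New therapy day 70, end-of-study MRI day 80 | 56, censored | 0 |
| New therapy day 70, death day 150 | 56, censored | 0 |
| End-of-study MRI day 80, new therapy day 84 | 80, censored | 24 |
| Central progression on day-80 MRI | 80, event | 24 |
| No new therapy, death day 150 | 150, event | 94 |

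The zero arises when the disputed scan is the last usable one. The two 24-day rows differ in kind: in one the central time is censored, in the other it is an event. The table would print the same number for both.

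**3. The three readings of the sentence.**
- Per-patient subtraction of observed times: the first four rows look like agreed progressions.
- Only patients with an event on both assessments: the first five rows drop out, and the table does not say how many did.
- Differences between summary estimates: no patient-level disagreement is shown.

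Under none of them is the number of unconfirmed local progressions reported.

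**4. Size, under assumed inputs.** Take 45 patients with 38 local progressions, every rejected case censored at the disputed scan, and all other patients identical on both assessments.

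| Rejected | Zero differences | Same event status |
|---|---|---|
| 10% (4 of 38) | 45/45 | 41/45 = 91.1% |
| 20% (8 of 38) | 45/45 | 37/45 = 82.2% |
| 30% (11 of 38) | 45/45 | 34/45 = 75.6% |

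The rejection rates are not in the documents. The all-zero column also depends on every rejected case following a zero path.

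**5. NPFS versus CDFS.** Section 7.2.2 censors NPFS at the last neurologic assessment and CDFS at the last Karnofsky assessment. Under section 6.2.4, Karnofsky is scored every 28 days, and NANO every 2 cycles up to cycle 6, then every 3. Day 1 of cycle k falls on day 28(k − 1) + 1, ignoring visit windows.
- No event on either, data end after cycle 4 day 1: NANO day 57, Karnofsky day 85, difference 85 − 57 = 28 days.
- No event on either, data end after cycle 9 day 1: NANO day 169, Karnofsky day 225, difference 225 − 169 = 56 days.
- NPFS event day 57, CDFS censored day 85: tabulated as 28, but all that is known is that it exceeds 28.

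The first two reflect the visit schedule alone. They apply to patients still on treatment at data cut-off or lost before an end-of-study visit, since that visit includes both assessments.

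**The case against.** The strongest reply is that the plan is silent on event status, which is not the same as ignoring it. Times to event can be read as limited to patients who had the event, and the word estimates is used elsewhere in section 8.2.2 for summary statistics. Kaplan-Meier PFS6, which uses event status, and the success rate, which includes freedom from progression at 6 months, are shown on both sources. Enough unconfirmed local progressions would separate them. A separate Central Review Charter (section 16.5.1.4) may say more and is not available here.

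Much of this stands, and it rules out four stronger readings:
- A reader might infer that a rejected progression is always scored as perfect agreement. No agreement measure is defined, and three of the seven worked patients do not give zero.
- A reader might infer that central time can never be later than local time. Later scans can exist: the end-of-study MRI (6.3.1), a repeat MRI at least 28 days later when progression is unclear (7.1.8), and equivocal progression that is later confirmed and dated back (7.2.5). Death is also an event.
- A reader might infer that this table is the only check of local against central assessment. The paired estimates in section 8.2.2 are also checks.
- A reader might infer that the go decision is made too favourable. The rule uses local calls, and early unconfirmed local progressions lower the local count of patients progression-free at 6 months, which works against a go.

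What the reply does not cover is the patient level. Paired estimates show net differences, in which local-only and central-only progressions can offset each other.

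**Conclusion.** The point holds as a gap in a descriptive secondary analysis. The sentence sets no rule for event status, and under any reading of it the table does not show how many local progressions central review left unconfirmed. With per-patient subtraction, a rejected progression gives 0 days when the disputed scan is the last one on or before new therapy. How often that happens cannot be derived from the documents; it depends on the rejection rate, on the timing of end-of-study MRI relative to new therapy, and on deaths. Where only one time is censored, the difference is at best a bound; where both are, it can reflect visit schedules alone.

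Severity is minor. The primary decision rule, the sample size and the Kaplan-Meier estimates do not change.

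**What to change.** Replace the sentence in section 8.2.2 with wording along these lines: *Event status will be cross-tabulated (both, local only, central only, neither), overall and at 6 months, with progression and death shown separately. The proportion of local progressions not confirmed centrally, and of central progressions not called locally, will be given. Differences in dates will be summarised only for patients with an event on both assessments. The same layout will be used for NPFS versus CDFS.*

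Two details are worth settling in the text. First, define confirmed as a central progression at any scan, so that a rejected progression followed by death (last row of the worked table) counts as unconfirmed even though both assessments have a PFS event. Second, give the 6-month table a category for central status unknown, because a rejected early progression is often censored centrally before 6 months.

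The cost is a few lines of SAP wording and one extra descriptive table from data already collected. It is best fixed before the central read is analysed, so that the handling of discordant patients is not chosen after the results are seen.

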3.2 Exclusion criteria

Specifics for groups A and B

- Prior RT with overlap of radiation fields with the planned RT in this study (Group A)
- Prior therapy for glioblastoma or anaplastic astrocytoma before surgery

Specifics for group C

- Discontinuation of TMZ for toxicity during first-line treatment
- RT or stereotactic radiosurgery is not allowed for the treatment of first recurrence prior to enrollment in this study

All groups

- Use of enzyme-inducing anti-epileptic drugs (EI-AED) within 7 days prior to the first dose of TG02
- History of ventricular arrhythmia or symptomatic conduction abnormality in past 12 months prior to registration

- Congestive heart failure (New York Heart Association Class III to IV, see Appendix C), symptomatic ischemia, uncontrolled by conventional intervention, or myocardial infarction within 6 months prior to enrollment
- 12-lead ECG with a prolonged QTc interval (males: > 450 ms; females: > 470 ms) as calculated by the Fridericia correction formula despite balancing of electrolytes at registration and/or discontinuing any drugs (for a time period corresponding to 5 half-lives) known to prolong QTc interval
- Known contraindication to imaging tracer or any product of contrast media
- MRI contraindications
- Known hypersensitivity to the active substance or any of the excipients in the TG02 formulation, dacarbazine and TMZ
- Concurrent severe or uncontrolled medical disease (e.g., active systemic infection, diabetes, hypertension, coronary artery disease) that, in the opinion of the Investigator, would compromise the safety of the patient or compromise the ability of the patient to complete the study
- Known human immunodeficiency virus infection or acquired immune deficiency syndrome
- Previous other malignancies, except for any previous malignancy which was treated with curative intent more than 3 years prior to enrollment, or adequately controlled limited basal cell carcinoma of the skin, squamous carcinoma of the skin or carcinoma in situ of the cervix

4 Trial Design

This is a three parallel group Phase Ib, open-labeled, non-randomized, multicenter study. Each group is described below and outlined in the diagram. All three groups will enroll independently.

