6.2.3.1 Day 1: prior to first dose of TG02

- Concomitant medications assessment
- Steroid dose. For corticosteroids, dose, frequency, dates of administration and route of administration must be recorded in the dedicated eCRF.
- Vital signs: blood pressure, pulse, temperature, weight
- Karnofsky Performance Status (KPS) (see Appendix E)
- Hematology: includes hemoglobin, hematocrit, total WBC count with differential (neutrophils and lymphocytes), and platelet count. If the registration hematology panel has been done within 72 h prior to first dose of TG02, it does not need to be repeated.
- Biochemistry: sodium, potassium, chloride, BUN, creatinine, total protein, albumin, AST and/or ALT, total bilirubin, alkaline phosphatase, calcium, magnesium, LDH, glucose, creatinine kinase and phosphate. If the registration biochemistry panel has been done within 72 h prior to first dose of TG02, it does not need to be repeated.
- Coagulation: PT, PTT and INR. If the registration coagulation panel has been done within 72 h prior to first dose of TG02, it does not need to be repeated.
- Adverse events assessment (see section 7.3.1)
- Optional translational research: 20 mL blood for soluble biomarker assessment
- **Prescription:** TG02 prescription (+ prophylaxis, see section 5.6.2)
- Blood sample for Pharmacokinetics (6 mL blood) for patients consented to the PK study just prior to TG02 administration.

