8.1.2 Randomization and stratifications

No randomization or stratification will be used in this study.

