Laboratory events of clinical significance (CS) will be reported on the adverse events CRFs and will be reported separately.

- Hematological parameters

The worst value of each hematological category will be identified and graded for each patient.

Frequencies and percentages of each category will be tabulated. A table with grade 3/4 frequencies and percentages will also be displayed. The frequencies and percentages of patients with at least one grade 1 or one grade 3 or 4 hematological toxicity will be presented.

- Biochemistry parameters

The worst value of each biochemical category will be identified and graded for each patient. Frequencies and percentages of each category will be tabulated. A table with grade 3/4 frequencies and percentages will be displayed. The frequencies and percentages of patients with at least one grade 1 or one grade 3 or 4 biochemistry toxicity will be presented.

- All adverse events

The worst grade of each AE item will be identified for each patient. Frequencies and percentages of each category will be tabulated. Tables with all grades, grades 3 or 4 and grades 5 frequencies and percentages will be displayed. The frequencies and percentages of patients with at least one grade 1 or one grade 3 or 4 or one grade 5 AE will be presented.

- Related AEs

The worst grade of each likely related AE item will be identified for each patient. Frequencies and percentages of each related AE category will be tabulated. Tables with related grades, grades 3 or 4 and grade 5 frequencies and percentages will be displayed. The frequencies and percentages of patients with at least one related grade 1 or one related grade 3 or 4 or one related grade 5 AE will be presented.

- SAEs and Related SAEs

After reconciliation with the SAEs listing extracted from the EORTC pharmacovigilance database, the worst grade of each (related) serious AE category will be identified for each patient. Frequencies and percentages of each category will be tabulated. Tables with all (related) grades, (related) grades 3 or 4 and (related) grades 5 frequencies and percentages will be displayed. The frequencies and percentages of patients with at least one (related) grade 1 or one (related) grade 3 or 4 or one (related) grade 5 SAE will be presented.

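### Group C safety tables tie baseline to a randomization that never takes place and show no worsening from baseline, so abnormalities present at entry are counted in the all-cause toxicity tables

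*Combined protocol and SAP*

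**What the plan says.** Section 8.2.2 (Group C, Safety and tolerability) gives the reporting periods: "The safety and tolerability analyses will be presented at baseline and up to 30 days after the last administration of study drug". It anchors baseline as follows: "Baseline will include all information recorded up to the nearest date prior to or at randomization". Exceptionally, when no such assessment exists, "the first assessment performed after randomization but before start of protocol treatment can be considered as baseline". It then states: "Baseline laboratory and AE grades will not be accounted for in whole treatment safety analyses".

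Section 8.1.2 says: "No randomization or stratification will be used in this study". Chapter 4 describes the design: "This is a three parallel group Phase Ib, open-labeled, non-randomized, multicenter study".

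The laboratory tables in section 8.2.2 use the worst value: "The worst value of each hematological category will be identified and graded for each patient". Biochemistry and adverse events follow the same pattern. Related AEs and related SAEs have their own tables, and clinically significant laboratory events are reported separately. No shift table or treatment-emergent summary is described.

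Section 6.2.3.1 requires a Group C hematology panel before the first dose on Day 1, with one waiver: "If the registration hematology panel has been done within 72 h prior to first dose of TG02, it does not need to be repeated". Biochemistry has the same waiver.

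For Groups A and B, section 8.2.2 gives no safety baseline. It says only that laboratory parameters are presented by clinical significance (CS vs NCS).

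**The concern.** With no control arm, a patient's own starting value is the only reference for judging whether a laboratory value or symptom changed on TG02. The plan's anchor for that value does not exist. Under the likeliest substitute (enrollment), the value closest to the first dose is usually not the baseline. The tables then do not use baseline to show change.

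At stake is how the safety profile reads. All Group C patients have had RT and at least one dose of TMZ (section 3.1), and corticosteroids are permitted (section 5.6.3), so some will enter with abnormal values. Cross-study comparison matters in this program: section 1.3.3.2 explains dose changes by AE rates above those in earlier myeloma studies, and section 1.3.2 lists the myeloma events as TEAEs. Tables without a treatment-emergent definition are not on that footing.

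**Working it through.** **The plan's own figure.** The plan gives no number on this point. Its only sized figure for Group C is the PFS-6 rule of at least 13 of 45. It reproduces: P(X ≥ 13 | 45, 0.20) = 0.0995 and P(X ≥ 13 | 45, 0.40) = 0.9554, within the stated 0.10 and 0.05. The rule counts progression and death, not grades, so nothing below changes it.

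**1. The anchor.** Baseline is at or before randomization (8.2.2), and there is no randomization (8.1.2). The candidates are enrollment and first dose. In Group C, registration and enrollment are one step (6.1.2), and up to 7 days may then pass before the first dose (6.1.3.3).

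**2. The Day 1 panel.** Marrow, renal and hepatic eligibility values must fall within 7 days before the first dose (3.1). The Day 1 panel is waived only if the registration panel was within 72 hours, that is 3 days. A registration panel taken more than 3 and up to 7 days before dosing must therefore be followed by a second pre-dose panel. If the anchor is enrollment and a registration panel exists, the fallback does not apply, so the second panel is not baseline. Section 8.2.2 gives an end to the treatment period (30 days after last dose) but no start, and AE collection begins at enrollment (7.3.1). Pre-dose values and events after enrollment are thus unclassified.

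**3. The two readings of the baseline sentence.** Take a patient with an abnormality at entry that is still present on Day 8.
- If baseline records are left out, the entry value is dropped, but the Day 8 value is on treatment and enters the worst-value table.
- If no adjustment is made, the Day 8 value enters the table as it stands.

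The patient is counted either way, and no table shows that the grade did not change.

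**4. Size.** For a given grade threshold, let b be the proportion at or above it at entry who stay there without worsening, and t the new-onset rate among the rest.
- Raw worst-grade rate = b + (1 − b)t
- Treatment-emergent rate = (1 − b)t
- Difference = b

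The documents give neither b nor t, so the values below are assumptions. Counts are per 45 patients, with t = 10%:

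| b (assumed) | Raw rate | Emergent rate | Raw count | Emergent count |
|---|---|---|---|---|
| 0% | 10.0% | 10.0% | 4.5 | 4.5 |
| 5% | 14.5% | 9.5% | 6.5 | 4.3 |
| 10% | 19.0% | 9.0% | 8.6 | 4.1 |
| 20% | 28.0% | 8.0% | 12.6 | 3.6 |
| 30% | 37.0% | 7.0% | 16.6 | 3.1 |

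For b = 10%: 0.10 + 0.90 × 0.10 = 0.19, against 0.90 × 0.10 = 0.09. The 45 is the efficacy number. The safety population is all treated patients (8.2.1), planned at no more than 50; at 50 the same row gives 9.5 and 4.5. The difference in percentage points does not depend on the denominator, and is zero for any grade that no patient has at entry.

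**5. Where b can be above zero.** Section 3.1 limits WBC, ANC (at least 1.5 × 10⁹/L), platelets (at least 100 × 10⁹/L), hemoglobin (at least 10 g/dL), bilirubin, ALT/AST (at most 2.5 × ULN) and creatinine clearance. For severe grades of these parameters b should be near zero. It is open for low grades, and at any grade for lymphocytes and glucose, which are measured but have no entry limit.

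**6. Baseline shown separately.** Suppose 9 of 45 patients have grade 3/4 at baseline and 14 of 45 on treatment (assumed). If all 9 persist, new cases are 14 − 9 = 5. If none persists, they are 14. The two marginal tables cannot distinguish these.

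**The case against.** The other side has several good points.

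- Baseline is displayed as its own period, so entry grades are visible at group level. That stands, but step 6 shows it cannot tell who worsened.
- A table of all events does not attribute them to TG02. The investigator judges relatedness for every AE (7.3.1), and related AEs and SAEs have their own tables. That stands for adverse events. The hematology and biochemistry tables have no relatedness version, although the plan calls their counts toxicity. The clinical-significance flag is a judgment, not a change from baseline.
- Entry limits largely close off severe neutropenia, thrombocytopenia, anemia and transaminase elevation. That stands and narrows the point.
- The gap between enrollment and first dose is short, and a pre-dose panel matters only if it is the patient's worst value. That also stands.

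A reader might go further and infer that pre-existing cytopenias and pre-dose values will be reported as TG02 toxicity. The documents do not support that: the tables are all-cause, severe cytopenias other than lymphopenia are largely excluded at entry, and if baseline records are left out, values classed as baseline do not count.

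A reader might also infer that this affected dose decisions. The Group C starting dose fell twice, from 250 to 200 to 150 mg. The drivers named in section 1.3.3.2 were neutropenia and, for the second step, also liver enzyme elevation; ANC and ALT/AST have entry limits. Section 8.1.1 gives no laboratory reason for the later halt to escalation.

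**Conclusion.** The point holds as a defect of definition and presentation. The Group C safety baseline has no valid anchor, the last pre-dose value is baseline only by exception if the anchor is read as enrollment, and no planned table shows within-patient worsening. Under either reading of the baseline sentence, a persisting entry abnormality is counted in the all-cause tables.

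The inflation equals the persisting baseline prevalence, on the assumption that those patients do not worsen further. That prevalence is not in the documents: 10% is an illustration, and the result simply returns the assumption. The grade 3/4 lymphocytopenia rates of 27% and 10% in section 1.1 come from a cited trial during first-line treatment and cannot stand in for prevalence at relapse.

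The reach is limited to descriptive safety reporting. Group A and B DLTs require clinical significance and a reasonable possibility of relatedness (5.2.1.1, 5.2.1.2). The Group C starting-dose rule counts patients who leave treatment for reasons other than progression (5.2.1.3). The PFS-6 rule does not use grades. The change should be made before the safety tables are programmed, but no decision rule depends on it.

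**What to change.** In section 8.2.2:

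1. Define baseline as the last value before the first TG02 dose, replacing the reference to randomization and the exceptional fallback.
2. Define the on-treatment period as first TG02 dose to 30 days after last dose.
3. Replace the sentence on baseline grades with treatment-emergent summaries (grade worse than baseline) and, for hematology and biochemistry, tables of baseline grade by worst on-treatment grade. Show them alongside the existing raw worst-grade tables; which set leads is a matter of preference.
4. Use the same baseline definition for Groups A and B, which currently have none.

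The cost is SAP wording and some extra programming. All the data are already collected.
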